#### **10.5. Other Safety Measures**

All collected measures and assessments will be listed. No other safety analyses have been prospectively defined. If, however, after study results are reviewed, they will be fully described and documented in the final clinical study report. The SAP does not need to be amended to complete any other safety measures identified as post-hoc.

### **11. PHARMACOKINETIC (PK) ANALYSES**

All PK analyses will be conducted using the PK population and actual treatment a subject received. Plasma concentration will be measured in this population, blood samples will be collected 2 hours ( $\pm$  30 minutes) after study medication dosing at the clinical site at Visit 4/Day 15 and Visit 6/Day 84.

Descriptive summary statistics of concentration data by visit/time and treatment will include n, mean, standard deviation, coefficient of variation (%CV), median, minimum, maximum, and geometric mean.

For each analyte, the plasma concentration at each timepoint will be analyzed using analysis of variance (ANOVA), considering treatment as fixed effect. For each treatment, LS means will be calculated. Mean differences between the test treatments and the comparator (timolol 0.5%) and the corresponding 90% CI will be calculated.

All available concentration-time data will be listed by treatment.

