Nonclinical pharmacology, pharmacokinetics, and toxicology studies were conducted in support of the development of timolol (topical ocular route) and nebivolol (systemic route). Based on the results of the 28-day and 6-month repeat dose toxicology studies in albino rabbits, the pharmacological and toxicological data for BTQ-1901-A, BTQ-1901-B, and BTQ-1902 are considered adequate to support their safe clinical use for this initial Phase 2 clinical trial. There were no significant macroscopic or microscopic findings observed in rabbits dosed with nebivolol 1.0% ophthalmic suspension (BTQ-1901-B) 4 times daily for 28 days or twice daily (BID) for 6 months, or with timolol 0.5% ophthalmic suspension (BTQ-1902) BID for 6 months. Moreover, systemic accumulation of nebivolol 1.0% and timolol 0.5% was very low after the 6-month treatment period (around the lower limits of quantification [LLOQ]). Therefore, ocular instillation of BTQ-1901 or BTQ-1902 twice daily to subjects with a maximum clinical concentration of 1.0% nebivolol or 0.5% timolol for up to 12 weeks is considered safe for the initial Phase 2 clinical study.

BTQ-1901 and BTQ-1902 ophthalmic suspensions are topical treatments for POAG or OHT that have not been previously evaluated in clinical trials. The planned first in human (FIH) study is a randomized, multicenter, observer-masked study to compare the safety and efficacy of BTQ-1901-A, BTQ-1901-B, and BTQ-1902 to timolol 0.5% ophthalmic solution in subjects with POAG or OHT in both eyes over a 12-week (84-day) treatment period. For additional information regarding BTQ-1901 and BTQ-1902 ophthalmic suspensions, please refer to the Investigator's Brochure.

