## **5.3. Randomization and Masking**

A total of 240 eligible subjects will be randomized in a 1:1:1:1 ratio into 1 of 4 treatment arms and receive 1 drop in each eye BID, morning, and evening, for 84 days:

- BTQ-1901-A (nebivolol 0.5% ophthalmic suspension) (N = 60)
- BTQ-1901-B (nebivolol 1.0% ophthalmic suspension) (N = 60)
- BTQ-1902 (timolol 0.5% ophthalmic suspension) (N = 60)
- Timolol 0.5% ophthalmic solution (N = 60) [active comparator]

A randomized block design will be used, and the randomization will be created by a biostatistician independent of the trial. Randomization will not be stratified by any factors.

If subjects meet eligibility criteria at Visit 1/Screening as well as at Visit 3/Qualification/Baseline, sites will access the Interactive Web Response System (IWRS) to randomize subjects to study treatment and assign the study medication kit to be dispensed. The drug kit and randomization numbers will be recorded in the subject's eCRF. Study medication from the IWRS-assigned kit will be dispensed to the subject after initial dosing at the study site on Day 1 (Visit 3/Qualification/Baseline). The study will be observer masked.

Rules for unmasking a subject for safety reasons are fully described in the protocol and not repeated herein this SAP.

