#### 7.1.4. Pharmacokinetic Population (PK)

The PK population will consist of the subjects who were randomized, dosed, and have at least one PK value. It is planned that plasma concentration will be measured in a subset of 40 subjects. Subjects who are members of the PK population will be analyzed as treated.

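### SAP 11 compares plasma concentrations as untransformed mean differences with no rule for results below LLOQ; if BTQ-1902 clearly lowers timolol exposure and variability is high, the 90% CI under-covers and is less able to show it

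*SAP*

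**What the plan says.** SAP section 11 sets out the whole PK analysis. For each analyte, "the plasma concentration at each timepoint will be analyzed using analysis of variance (ANOVA), considering treatment as fixed effect". LS means follow, and then: "Mean differences between the test treatments and the comparator (timolol 0.5%) and the corresponding 90% CI will be calculated". The descriptive list in the same section includes "coefficient of variation (%CV), median, minimum, maximum, and geometric mean". No transformation or ratio is mentioned, and the section does not say which arms enter the model for each analyte.

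On numbers, SAP section 7.1.4 says: "It is planned that plasma concentration will be measured in a subset of 40 subjects". The trial as a whole is "randomized in a 1:1:1:1 ratio into 1 of 4 treatment arms" (SAP section 5.3), but the split of the PK subset by arm is not given.

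On levels, Protocol section 4 reports that "systemic accumulation of nebivolol 1.0% and timolol 0.5% was very low after the 6-month treatment period", and places those levels around the LLOQ. The paragraph opens "Based on the results of the 28-day and 6-month repeat dose toxicology studies in albino rabbits", so this is animal evidence on the suspensions. The same section postulates that the smaller drop of the new products, about 11 μL, may mean less systemic absorption.

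No rule for results below LLOQ appears in either document. Protocol section 11.7 leaves PK detail to the SAP, and the missing-data rules in SAP section 7.3.2 deal with dates, baseline and efficacy data. Protocol section 9.3 refers to a Study Manual for further PK detail; it is not among the documents.

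**The concern.** Plasma concentrations cannot be negative, are usually right-skewed, and tend to vary more as their level rises. The usual estimand is therefore a ratio of geometric means, and by listing %CV and the geometric mean SAP section 11 already leans that way in its summaries. The inferential step then changes scale and gives a difference in concentration units, which does not read as relative exposure.

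The comparison that matters is BTQ-1902 against timolol solution: both contain timolol 0.5%, so the contrast bears directly on the reduced-absorption rationale. It is the only planned comparison of plasma exposure with a confidence interval. An interval that performs worse as the true reduction grows is a poor choice for it. Without a below-LLOQ rule, the geometric mean and the model input also depend on a decision that could be taken after the data are seen.

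**Working it through.** The documents give no PK power, precision or coverage figure, so there is none to reproduce. Coverage was simulated.

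**Inputs from the documents:** ANOVA on concentration with treatment as the only effect; difference in means with a 90% CI; 40 PK subjects in total.

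**Assumptions, not in the documents:** 10 subjects per arm (40/4, an even split); lognormal concentrations with the same CV in both arms; CV 50% to 150%; true BTQ-1902/solution ratio r from 1 to 0.3; only the two timolol arms fitted; all results quantifiable unless stated.

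**Formulas.** Log-scale SD: s = sqrt(ln(1 + CV²)); at CV 120%, s = sqrt(ln 2.44) = 0.944. True mean difference, with the comparator geometric mean set to 1: (r − 1)·exp(s²/2). Interval: difference ± t(0.95; 18 df) × pooled SE, computed on the raw and on the log scale. A reduction is shown when the upper limit is below zero.

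**Step 1: coverage of the nominal 90% CI, 10 per arm.**

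| True ratio | Raw, CV 50% | Raw, CV 100% | Raw, CV 150% | Log, all CVs |
|---|---|---|---|---|
| 1 | 90% | 91% | 92% | 90% |
| 0.75 | 90% | 90% | 90% | 90% |
| 0.5 | 89% | 87% | 85% | 90% |
| 0.3 | 87% | 84% | 80% | 90% |

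With 20 per arm the raw-scale loss is smaller: 89% to 86% at ratio 0.5 and 88% to 83% at ratio 0.3 over the same CVs.

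**Step 2: direction.** At ratio 0.3 and CV 120%, the raw interval lies wholly above the true difference, understating the reduction, in about 17% of trials, and wholly below it in about 1%. The nominal rate is 5% each way.

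**Step 3: chance of showing a reduction.**

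| Ratio, CV | Raw | Log |
|---|---|---|
| 0.5, 120% | 38% | 47% |
| 0.3, 80% | 95% | 98% |
| 0.3, 120% | 73% | 86% |
| 0.3, 150% | 60% | 77% |

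**Step 4: results below LLOQ.** Suppose LLOQ is half the comparator geometric mean and CV is 120%. The comparator share below LLOQ is Φ(ln 0.5 / 0.944) = 23%. At ratio 0.5 the test-arm share is Φ(0) = 50%; LLOQ/2 on the log scale still covers 90% and shows a reduction in 44% of trials, against 38% for raw data with zeros. At ratio 0.3 the test-arm share is Φ((ln 0.5 − ln 0.3)/0.944) = Φ(0.54) = 71%, and log-scale coverage falls to about 85%. A fallback is therefore needed.

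**Step 5: geometric mean.** One zero makes it zero, or not computable through logs. If a fraction f of results were entered as zero, a 10-subject arm would contain at least one with probability 1 − (1 − f)^10: 40% at f = 5%, 65% at 10%, 89% at 20%.

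**Step 6: which arms enter.** If all four arms were fitted for timolol and the two nebivolol arms sat at zero, they would add degrees of freedom but no variance and would halve the error mean square. For two equal normal arms, coverage is then 2·T₁₈(t(0.95; 36 df)/√2) − 1 = 75%. SAP section 11 neither says this will be done nor excludes it.

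**The case against.** A reader might infer that concentrations near LLOQ are to be expected, that untransformed ANOVA therefore under-covers, and that the planned geometric mean cannot be computed. The documents do not support that. The scale alone does no harm when the arms are alike: coverage is 90-92% at ratio 1, stays there when 5% to 50% of both arms are set to zero, and is 90% at ratio 0.75. A marked loss needs a large reduction together with a high CV, and the documents give neither figure. Levels near LLOQ in humans are an inference from rabbits dosed with the suspensions; nothing is said about the timolol solution. Neither document says that a result below LLOQ is entered as zero, and the Study Manual or the external laboratory may hold a convention.

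Three further points stand. The power gain in step 3 assumes that every result is quantifiable, so it cannot be carried over to a setting with many results below LLOQ. Unequal variance is the smaller part of the mechanism: for normal data with an SD ratio of 0.3 and 10 per arm, coverage is still 88.5%, so most of the loss comes from the assumed skew, and an unequal-variance interval would not cure it. And PK has no hypothesis, margin or decision rule; it lies outside the hierarchy, and SAP section 7.5 calls all other comparisons exploratory. Medians, geometric means and listings are already planned.

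What the objection leaves in place is that SAP section 11 states a method whose performance worsens in the situation the protocol hopes for, that its inferential scale does not match its descriptive one, and that the rule for results below LLOQ is missing.

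**Conclusion.** The concern holds in conditional form. If timolol exposure with BTQ-1902 is about half that with the solution or less, and variability is high, the planned 90% CI covers about 85-89% (ratio 0.5) or 80-87% (ratio 0.3) for CVs of 50% to 150%, errs mainly towards understating the reduction, and at CV 120% gives up about 9 (47 − 38) to 13 (86 − 73) percentage points of the chance to show it. With similar arms nothing is lost. The size rests on an even split of the 40 subjects, lognormality, the CV and the ratio, all assumed, and on all results being quantifiable. Difficulty with the geometric mean is conditional on zeros being entered. The change is worth making because it is cheap and improves the one like-for-like exposure comparison. The primary efficacy conclusion is untouched.

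**What to change.** In SAP section 11:

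- For each analyte, fit the model to log concentration using only the arms that contain that analyte. For timolol, report the geometric mean ratio of BTQ-1902 to timolol solution with its 90% CI at each visit. Nebivolol has no contrast with the solution, which does not contain it.
- Set results below LLOQ to LLOQ/2 for the log analysis and the geometric mean, and show the number below LLOQ by arm and visit.
- If more than half of either arm is below LLOQ, report only medians and the proportion quantifiable.

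The cost is a few lines of SAP text and a log transform in the program, with no new samples or visits. The downside is that LLOQ/2 is a convention, which is why the counts must stand beside it, and the gain shrinks or disappears when many results are below LLOQ. The change belongs before unmasking, when SAP section 3.1 says the plan is to be final. If that point has passed, the log-scale analysis can be added beside the planned one and labelled post hoc, as SAP section 3.2 allows.
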